#### **5.4 Participant Withdrawal/Discontinuation Criteria**

Participants may discontinue study treatment at any time for any reason or be dropped from the study treatment at the discretion of the investigator should any untoward effect occur. In addition, a participant may be discontinued from study treatment by the investigator or the Sponsor if study treatment is inappropriate, the trial plan is violated, or for administrative and/or other safety reasons. Specific details regarding procedures to be performed at study treatment discontinuation are provided in Section 7.1.4 – Other Procedures.

A participant must be discontinued from study treatment but continue to be monitored in the study for any of the following reasons:

- The participant or participant's legally acceptable representative requests to discontinue study treatment
- Confirmed radiographic disease progression outlined in Section 7.1.2.6
- Any progression or recurrence of any malignancy, or any occurrence of another malignancy that requires active treatment
- Unacceptable adverse experiences as described in Section 5.2.2.
- The participant has a medical condition or personal circumstance which, in the opinion of the investigator and/or sponsor, placed the participant at unnecessary risk from continued administration of study treatment.
- The participant has a confirmed positive serum pregnancy test
- Noncompliance with study treatment or procedure requirements
- Recurrent Grade 2 pneumonitis
- Discontinuation of treatment may be considered for participants who have attained a confirmed complete response (CR) and have been treated for at least 8 cycles (at least 24 weeks), receiving at least 2 doses of pembrolizumab beyond the date when the initial CR was declared. These participants may be eligible for second course treatment described in Section 5.2.5.
- The participant is lost to follow-up
- Completion of 35 treatments (approximately 2 years) with pembrolizumab

Note: The number of treatments is calculated starting with the first dose. Participants who stop the combination or pembrolizumab after receiving 35 doses may be eligible for retreatment if they progress after stopping study treatment provided they meet the requirements detailed in Section 5.2.3. Participants may be retreated in the Second Course Phase (Retreatment) for up to an additional 17 cycles (approximately 1 year).

- Administrative reasons

### **5.5 Participant Replacement Strategy**

Additional patients will be recruited to meet the samples size required

### **5.6 Clinical Criteria for Early Trial Termination**

Early trial termination will be the result of the criteria specified below:

1. Unacceptably high incidence of toxicities among subjects enrolled in this or other studies, as assessed by an internal safety monitoring committee
2. Objective evidence of progressive disease as determined by CT scan and/or X-ray and/or ultrasound and/or clinical examination
3. Clinical decision by the investigator that continued participation in the trial is contrary to the patient's best interests
4. Quality or quantity of data recording is inaccurate or incomplete
5. Poor adherence to protocol and regulatory requirements
6. Plans to modify or discontinue the development of the study drug

In the event of Merck decision to no longer supply study drug, ample notification will be provided so that appropriate adjustments to participant treatment can be made.

**6.0 TRIAL FLOW CHART**

**6.1 Initial Treatment with Study Drug**

Trial Period:	Screening Phase	Treatment Cycles (3-week Cycles)								End of Treatment	Post-Treatment			
Treatment Cycle/Title:	Screening	1	2	3	4	To be repeated beyond 8 cycles				Discon	Safety Follow-up	Follow Up Visits	Survival Follow-Up a	
Scheduling Window (Days) b :	-28 to -1		± 3	± 3	± 3	± 3	± 3	± 3	± 3	± 3	At time of Discon	30 days post last dose	Every 8 weeks post	Every 12 weeks
Administrative Procedures														
Informed Consent	X													
Inclusion/Exclusion Criteria	X													
Demographics and Medical History	X													
Prior and Concomitant Medication Review	X	X	X	X	X	X	X	X	X	X	X	X		
Trial Treatment Administration		X	X	X	X	X	X	X	X					
Post-study anticancer therapy status												X		
Survival Status a														X
Clinical Procedures/Assessments														

Trial Period:	Screening Phase	Treatment Cycles (3-week Cycles)								End of Treatment	Post-Treatment		
Treatment Cycle/Title:	Screening	1	2	3	4	To be repeated beyond 8 cycles				Discon	Safety Follow-up	Follow Up Visits	Survival Follow-Up a
Scheduling Window (Days) b :	-28 to -1		± 3	± 3	± 3	± 3	± 3	± 3	± 3	At time of Discon	30 days post last dose	Every 8 weeks post discon	Every 12 weeks
Review Adverse Events c	X	X	X	X	X	X	X	X	X	X	X	X c	
Full Physical Examination	X									X			
Directed Physical Examination		X	X	X	X	X	X	X	X				
Height d , Weight and Vital Signs (T, P, RR, BP)	X	X	X	X	X	X	X	X	X	X			
ECOG Performance Status e	X	X	X	X	X	X	X	X	X	X			
Laboratory Procedures/Assessments: analysis performed by LOCAL laboratorym													
Pregnancy Test – Urine or Serum β-HCG f	X												
PT/INR and aPTT g,h	X e		X		X		X		X	X			
CBC with Differential g	X e		X	X	X	X	X	X	X	X	X		
Chemistry and Liver Panel g	X e		X	X	X	X	X	X	X	X	X		
Urinalysis g,h	X e		X		X		X		X	X			
T3, FT4 and TSH g,h	X e		X		X		X		X	X			
Efficacy Assessment													
CT Chest/Abdomen/Pelvis i	X					X i				X j			
Bone Scan k	X					X k							
Brain Imaging l	X					X l							

Trial Period:	Screening Phase	Treatment Cycles (3-week Cycles)								End of Treatment	Post-Treatment			
Treatment Cycle/Title:	Screening	1	2	3	4	To be repeated beyond 8 cycles				Discon	Safety Follow-up	Follow Up Visits	Survival Follow-Upa	
Scheduling Window (Days)b:	-28 to -1		± 3	± 3	± 3	± 3	± 3	± 3	± 3	± 3	At time of Discon	30 days post last dose	Every 8 weeks post discon	Every 12 weeks
CENTRAL Laboratory Assessments														
Archival or Newly Obtained Tissue Collection	X										X n			
Correlative Studies Blood Collection m	X			X				X			X			

- a. In subjects who experience PD or starts a new anti-cancer therapy, contact should be made (example: by telephone) approximately Q12W to assess for survival status. Updated survival status may be requested by the Sponsor at any time during the course of study. Upon Sponsor notification, all participants who do not/will not have a scheduled study visit or study contact during the Sponsor defined time period will be contacted for their survival status (excluding participants that have a death event previously recorded).
- b. Cycle 1 treatment must be given within 3 days of treatment allocation. The window for each visit is  $\pm 3$  days unless otherwise noted. If dosing is delayed due to administrative reasons, the subsequent dosing visit should be re-calculated to account for the every 3 week dosing visit.
- c. SAEs will be followed through 90 days following cessation of treatment, or 30 days following cessation of treatment if the subject initiates a new anticancer therapy, whichever is earlier. All protocol specific ECIs will be collected throughout the study as listed in Section 7.2.3.2. If any of the ECI criteria are met, collect the details until the ECIs resolve.
- d. Height will be measured at screening only.
- e. ECOG Performance Status and laboratory test for screening and determining eligibility are to be performed within 10days prior of the first dose of trial treatment except thyroid test, which may performed within 28days.
- f. For women of reproductive potential, a serum pregnancy test should be performed within 72 hours prior to receiving the first dose of study medication (Cycle 1 Day 1). Subject must be excluded/discontinued in the event of a positive results.
- g. After Cycle 1, laboratory samples can be collected up to 72 hours prior to the scheduled time point. CBC with differential, chemistry panel and liver panel to be performed every cycle. Details can be found in Section 7.1.3 Laboratory Procedure/Assessments. Liver panel to include albumin, ALT, AST, total bilirubin, alkaline phosphatase and total protein.
- h. While on treatment, PT/INR and aPTT, UA and thyroid function tests will be performed every other cycle.
- i. Screening tumour imaging will be performed within 28 days prior to treatment allocation. Imaging at screening should include chest, abdomen, and pelvis. The first on-study imaging time point will be performed at 9 week ( $\pm 7$  days) calculated from the date of treatment allocation and will be continue to be performed Q9W ( $63\pm 7$  days) in the first year, Q12W ( $84\pm 7$ days) in the second year of therapy.
- j. If previous imaging was obtained within 4 weeks prior to the date of discontinuation, then imaging at treatment discontinuation is not mandatory.
- k. Only for those with a history of bone metastases, to be repeated Q9W ( $63\pm 7$  days) from treatment allocation in first year, Q12W ( $84\pm 7$ days) in second year of therapy.
- l. Only for those with known brain metastases, CT or MRI brain to be repeated Q9W ( $63\pm 7$  days) from treatment allocation in first year, Q12W ( $84\pm 7$ days) in second year of therapy.
- m. Blood for correlative studies should be collected at Cycle 3, at Cycle 6 and again at discontinuation (end of treatment).
- n. Tissue collection through core needle biopsy (CNB) or excisional biopsy (EB) may be performed when progressive disease is confirmed.

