### **5.2.2 Dose Modification and toxicity management for immune-related AEs associated with pembrolizumab**

AEs associated with pembrolizumab exposure may represent an immunologic etiology. These immune-related AEs (irAEs) may occur shortly after the first dose or several months after the last dose of pembrolizumab treatment and may affect more than one body system simultaneously. Therefore, early recognition and initiation of treatment is critical to reduce complications. Based on existing clinical study data, most irAEs were reversible and could be managed with interruptions of pembrolizumab, administration of corticosteroids and/or other supportive care. For suspected irAEs, ensure adequate evaluation to confirm etiology or exclude other causes. Additional procedures or tests such as bronchoscopy, endoscopy, skin biopsy may be included as part of the evaluation. Based on the severity of irAEs, withhold or permanently discontinue pembrolizumab and administer corticosteroids. Dose modification and toxicity management guidelines for irAEs associated with pembrolizumab are provided in Table 2).

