#### **7.1.5.3.2 Follow-up Visits**

Participants who discontinue study treatment for a reason other than disease progression will move into the Follow-Up Phase and should be assessed every 9 weeks ( $63 \pm 7$  days) by radiologic imaging to monitor disease status. After 1 year, the imaging time point will occur every 12 weeks ( $\pm 7$  days). Every effort should be made to collect information regarding disease status until the start of new anti-cancer therapy, disease progression, death, end of the study or if the participant begins retreatment with pembrolizumab as detailed in Section 5.2.3. Information regarding post-study anti-cancer treatment will be collected if new treatment is initiated.

Participants who are eligible to receive retreatment with pembrolizumab according to the criteria in Section 5.2.3 will move from the follow-up phase to the Second Course Phase when they experience disease progression.

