#### **7.1.5.3.3 Survival Follow-up**

Participants who experience confirmed disease progression or start a new anticancer therapy, will move into the Survival Follow-Up Phase and should be contacted by telephone every 12 weeks to assess for survival status until death, withdrawal of consent, or the end of the trial, whichever occurs first.

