- All AEs meeting serious criteria, from the time of treatment allocation/randomization through 90 days following cessation of study treatment, or 30 days following cessation of study treatment if the participant initiates new anticancer therapy, whichever is earlier must be reported by the investigator.
- All pregnancies and exposure during breastfeeding, from the time of treatment allocation/randomization through 120 days following cessation of study treatment, or 30 days following cessation of study treatment if the participant initiates new anticancer therapy must be reported by the investigator.
- Additionally, any SAE brought to the attention of an investigator at any time outside of the time period specified above must be reported immediately by the investigator if the event is considered to be drug-related.

Investigators are not obligated to actively seek AE or SAE or other reportable safety events in former study participants. However, if the investigator learns of any SAE, including a death, at any time after a participant has been discharged from the study, and he/she considers the event to be reasonably related to the study treatment or study participation, the investigator must promptly notify Merck.

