#### **7.2.3.2 Events of Clinical Interest**

Selected non-serious and serious adverse events are also known as Events of Clinical Interest (ECI) and must be reported within 2 working days to Merck Global Safety. (Attn: Worldwide Product Safety; [contact]).

For the time period beginning when the consent form is signed until treatment allocation/randomization, any ECI, or follow up to an ECI, that occurs to any participant must be reported within 2 working days to Merck Global Safety if it causes the participant to be excluded from the trial, or is the result of a protocol-specified intervention, including but not limited to washout or discontinuation of usual therapy, diet, placebo treatment or a procedure.

For the time period beginning at treatment allocation/randomization through 90 days following cessation of treatment, or 30 days following cessation of treatment if the participant initiates new anticancer therapy, whichever is earlier, any ECI, or follow up to an ECI, whether or not related to Merck product, must be reported within 2 working days to Merck Global Safety.

Events of clinical interest for this trial include:

1. an overdose of Merck product, as defined in Section 7.2.1 - Definition of an Overdose for This Protocol and Reporting of Overdose to the Sponsor, that is not associated with clinical symptoms or abnormal laboratory results.
2. an elevated AST or ALT lab value that is greater than or equal to 3X the upper limit of normal and an elevated total bilirubin lab value that is greater than or equal to 2X the upper limit of normal and, at the same time, an alkaline phosphatase lab value that is less than 2X the upper limit of normal, as determined by way of protocol-specified laboratory testing or unscheduled laboratory testing.\*

\*Note: These criteria are based upon available regulatory guidance documents. The purpose of the criteria is to specify a threshold of abnormal hepatic tests that may require an additional evaluation for an underlying etiology.

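### SAE capture runs to day 90, but after about day 30 nothing in the schedule asks about SAEs in patients who stopped for confirmed progression and are not on new therapy

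*Protocol*

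**What the plan says.** **The SAE window.** Note c to both flow charts (Sections 6.1 and 6.2) states that "SAEs will be followed through 90 days following cessation of treatment". It then shortens this period to 30 days for anyone who starts new anticancer therapy, taking the earlier of the two dates. Sections 7.2 and 7.2.3.1 set the same reporting window. Section 1.0 gives 90 days of SAE monitoring for each subject and mentions no exception. Section 7.1.5.3.1 asks for SAEs within 90 days, or before new therapy begins, to be followed and recorded.

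**The schedule.** In chart 6.1 the row "Review Adverse Events" is marked at screening, every cycle, discontinuation, the 30-day Safety Follow-up and the Follow Up Visits. It is blank under Survival Follow-Up. Section 7.1.5.3.2 limits the Follow-Up Visits: "Participants who discontinue study treatment for a reason other than disease progression will move into the Follow-Up Phase". Under Section 7.1.5.3.3, patients with confirmed progression or new therapy go to Survival Follow-Up, where they "should be contacted by telephone every 12 weeks to assess for survival status". Note a describes the same contact. In chart 6.2 (second course) the last mark in the adverse event row is at the 30-day visit.

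**Events of clinical interest (ECIs).** Note c has ECIs collected for the whole study and cites Section 7.2.3.2. That section runs only "through 90 days following cessation of treatment, or 30 days following cessation of treatment if the participant initiates new anticancer therapy", again taking the earlier of the two.

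**The concern.** A capture window works only if someone is scheduled to ask during it. Section 5.2.2 says that immune-related events "may occur shortly after the first dose or several months after the last dose of pembrolizumab treatment", so days 31 to 90 are a period in which the protocol itself expects late toxicity.

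Deaths will surface through the survival call. A non-fatal SAE in a patient who has progressed reaches the database only if it comes to the site's attention by another route. Patients who stop without progression are asked at their Follow-Up Visits. Ascertainment therefore differs by outcome, and the SAE summary in Section 8.7.2 would mix patients with different intensity of enquiry.

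The two wording conflicts matter for a simpler reason: sites applying different sections would collect different events.

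**Working it through.** The plan gives no figure to reproduce here, so the check is an alignment of the passages plus simple timing.

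**1. Adverse event row by column.** Each chart has 13 columns: screening, cycles 1 to 8, discontinuation, Safety Follow-up, Follow Up Visits and Survival Follow-Up. The last four cells read:

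| Chart | Discontinuation | Safety Follow-up (day 30) | Follow Up Visits | Survival Follow-Up |
|---|---|---|---|---|
| 6.1 initial course | X | X | X (note c) | blank |
| 6.2 second course | X | X (note c) | blank | blank |

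**2. Who is asked, and when.**
- Part of the SAE window after the 30-day visit: (90 − 30)/90 = 60/90 = 67%.
- Stopped without progression, initial course: the first Follow-Up Visit is at 8 × 7 = day 56 (chart) or 9 × 7 = day 63 (Section 7.1.5.3.2). Both fall in days 31 to 90 and carry adverse event review.
- Stopped for confirmed progression: the first survival call is at 12 × 7 = day 84 if counted from the end of treatment. It is inside the window but covers survival only. Section 7.1.5.3.3 does not say where the 12 weeks start. Counted from the 30-day visit, the call would be at 30 + 84 = day 114, after the window.

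**3. Who is affected.** A patient with progression who starts new therapy by day 30 has a window that closes at day 30, so there is no gap. The gap concerns those with progression and no new therapy.

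**4. SAE cut-off when new therapy starts between days 30 and 90.** Take an SAE on day 45 and new therapy on day 60.
- Note c, Sections 7.2 and 7.2.3.1: new therapy has started, and the earlier of 90 and 30 is day 30. Read literally, the SAE is outside the window.
- Section 7.1.5.3.1: the SAE came before new therapy, so it is inside.

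On the literal reading, an event that was reportable on day 45 falls out of the window on day 60.

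**5. ECI period.** Note c gives the whole study; Section 7.2.3.2 gives 90 or 30 days. Both cannot apply.

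**6. Can the number affected be derived?** No. The protocol states neither the expected share stopping for progression nor the share on new therapy by day 30. The following is illustration only. The 6-month PFS of 24% quoted in Section 4.2.1.1 from an earlier phase 1b study in triple-negative disease would give 44 × (1 − 0.24) = 33.4 patients progressed or dead by month 6. If 0%, 50% or 90% of 33 were on new therapy by day 30, then 33, 16.5 or 3.3 would have an open window without a scheduled enquiry. Assuming 22 to 40 patients with progression, the range is 22 × 0.10 = 2.2 up to 40 × 1.00 = 40. That is too wide to serve as an estimate.

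**The case against.** The strongest reply is that the duty to capture SAEs does not depend on a mark in a chart. Sections 1.0, 7.1.5.3.1, 7.2 and 7.2.3.1 require SAEs to be monitored, recorded and reported whatever visit is scheduled. Section 7.1.2.1 allows assessment more often than the chart shows, when clinically indicated. Drug-related SAEs that reach the investigator are reportable at any time. Adverse events above Grade 1 found by the 30-day visit are followed until they resolve or new therapy starts. Section 5.4 keeps patients who stop treatment under monitoring in the study.

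This stands in part. A reader might infer that SAEs in days 31 to 90 are under-counted; the documents show a risk of incomplete ascertainment, not an undercount. These safeguards do not close the gap, however. They cover events already known or brought to the site's attention, and none schedules an enquiry about new ones.

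A reader might also take "Investigators are not obligated to actively seek AE or SAE or other reportable safety events in former study participants" as releasing sites from asking these patients. The sentence after it concerns people discharged from the study, and patients in Survival Follow-Up have not been discharged.

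The ECI conflict has little practical effect. Only two ECIs are defined. Overdose cannot newly arise once dosing has ended. The other is a pattern of liver laboratory values, and chart 6.1 schedules no liver panel after the 30-day visit. It remains a contradiction in the text.

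**Conclusion.** The point holds as a minor one. Followed as written, the schedule does not support the 90-day SAE window for patients who stop for confirmed progression and are not on new therapy. In the second course it supports it for nobody. The period without enquiry is 60 of the 90 days, and the consequence is a risk of missing non-fatal SAEs. Separately, the new-therapy SAE cut-off and the ECI period are each stated in two incompatible ways.

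Two larger readings are not supported. A reader might infer that the gap covers most of the trial. That borrows the 24% PFS of an earlier study in triple-negative disease, whereas this trial also enrols ER-positive patients. It counts deaths as if those patients still had an open window, and it equates RECIST progression with stopping, although treatment may continue past first progression. A reader might also put percentage points on the lost SAE incidence. That needs a share without new therapy and a late SAE rate, and the documents give neither.

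Safety is summarised descriptively in a single arm. No efficacy endpoint, sample size or error rate is affected. The reading rests on the column positions in the two charts and on Sections 7.1.5.3.2 and 7.1.5.3.3 being applied literally.

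**What to change.** 1. In Section 7.1.5.3.3 and note a of both charts, time the first survival telephone contact at or just after day 90 from the last dose. Add questions on SAEs since the 30-day visit, with onset dates and the start date of any new therapy. Later calls can stay survival only. Mark adverse event review (note c) for that contact in charts 6.1 and 6.2, and at the Follow Up Visits in chart 6.2.
2. Reconcile the SAE cut-off for patients who start new therapy between days 30 and 90, so that one window applies. The edit must cover note c in both charts and Sections 7.1.5.3.1, 7.2 and 7.2.3.1, with Section 1.0 checked for consistency. Changing note c alone would leave the other sections in conflict.
3. Reconcile note c with Section 7.2.3.2 so that one ECI window applies.

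The cost is protocol wording, a few chart marks and a few questions on a call that is already planned. It adds no visit or laboratory test. The downside is some additional SAE forms and possibly a slightly higher reported SAE rate.
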